9.1.4.1 Storage

The tablets should be stored at 25°C (77°F); excursions permitted to 15°C to 30°C (59°F to 86°F).

If a storage temperature excursion is identified, promptly return tipifarnib to controlled room temperature (25°C/77°F) and quarantine the supplies. Provide a detailed report of the excursion (including documentation of temperature monitoring and duration of the excursion) to mailto:[contact] ov for determination of suitability.

9.1.4.2 Stability

Shelf life dating is printed on the bottle label. Stability studies are ongoing. The manufacturer does not have stability data to support repackaging tablets. Dispense tablets in the original container.

9.1.5 Guidelines for Administration

See Section 6.0 for dose modifications and Section 5.0 Treatment section of the protocol for dosing and administration details.

Tipifarnib is administered orally twice daily with food. No dietary restrictions related to tipifarnib are required. Patients should administer their dose of tipifarnib with a meal as the presence of food has been shown to improve the absorption of tipifarnib, as well as to reduce variability in the pharmacokinetic profile.

Tablets should be swallowed whole with water. Tablets may be chewed or crushed if necessary. Use of a percutaneous endoscopic gastrostomy tube (G-tube) or nasogastric tube (NG) is allowed.

Crushed Tablets for Oral, G-Tube or NG Administration

- Tablets should be crushed with a commercial tablet crusher, transferred into a dosing cup/glass and crusher rinsed with water.
- Crushed tipifarnib tablets might have a bitter flavor profile. The crushed tablets can be mixed with the following liquids for oral administration: water, orange juice, apple juice, tomato juice, a protein shake or a dietary supplement drink (eg., Ensure®).
- Patients should be instructed to consume the mixture with a meal. Following consumption, the dosing cup or glass should be rinsed with water and each rinse completely swallowed to ensure the entire dose is consumed.
- Crushed tablets mixed with liquids intended for oral administration should be used within 2 hours of mixing. The mixing container should be rinsed and the rinse consumed as well.
- For NG or G-tube administration crushed tablets should be mixed with sterile swater.
- After completion of dosing, the NG or G-tube should be flushed with 10-20mL sterile water to ensure that the entire dose is delivered.
- Crushed tablets mixed with water intended for nasogastric or gastric tube administration should be used within 16 hours of mixing.

Unless otherwise contraindicated, subjects should be advised to be appropriately hydrated during the course of the study (e.g. drinking at least 8 glasses of water/day). Vomitted doses should not be made up. Missed doses should not be taken if it is more than 4 hours past the scheduled time. Patients should continue with the next scheduled dose.

9.1.6 Supplier:

Supplied by Kura Oncology and distributed by a Division of Cancer Treatment and Diagnosis the Pharmaceutical Management Branch (DCTD), NCI.

9.1.7 **Obtaining the Agent**

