3.5 Study Enrollment

Patient may be enrolled on the study once all eligibility requirements for the study have been met. Following a MATCH treatment assignment to a protocol, patients may be enrolled on the study once all eligibility requirements for the study have been met. Before enrolling a patient on study, the Study Chair or Vice Chair should be notified. Patients who give informed consent for the protocol in order to undergo screening for eligibility are not considered enrolled and should not be enrolled until the screening is completed and they are determined to meet all eligibility criteria. Study enrollment in Stage 2 of Pediatric MATCH (effective with Amendment #4 of APEC1621SC for patients enrolling on screening protocol) is outlined in section 3.1.3.

Patients enrolling onto APEC1621M will have a COG ID obtained through their prior enrollment onto the APEC1621SC screening protocol or a prior COG study. Patients must be enrolled within 2 weeks (14 days) of treatment assignment. Protocol therapy must start no later than 7 calendar days after the date of enrollment. Patients enrolling onto APEC1621M will have a COG ID obtained through their prior enrollment onto the screening protocol or from a prior COG study. Patients who are started on protocol therapy prior to study enrollment will be considered ineligible.

All clinical and laboratory studies to determine eligibility must be performed within 7 days prior to enrollment unless otherwise indicated in the eligibility section below.

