4.2.2 Concomitant Medications

- 4.2.2.1 Corticosteroids: Patients receiving corticosteroids who have not been on a stable or decreasing dose of corticosteroid for at least 7 days prior to enrollment are not eligible. If used to modify immune adverse events related to prior therapy, ≥ 14 days must have elapsed since last dose of corticosteroid (See Section 4.1.6.1.d).
- 4.2.2.2 Investigational Drugs: Patients who are currently receiving another investigational drug are not eligible.
- 4.2.2.3 Anti-cancer Agents: Patients who are currently receiving other anti-cancer agents are not eligible.
- 4.2.2.4 Anti-GVHD agents post-transplant:
 Patients who are receiving cyclosporine, tacrolimus or other agents to prevent graft-versus-host disease post bone marrow transplant are not eligible for this trial.
- 4.2.2.5 Patients who are currently receiving drugs that are strong inducers or inhibitors of CYP3A4/5 or UGT are not eligible. Strong inducers or inhibitors of CYP3A4/5 or UGT should be avoided from 14 days prior to the 1st dose of tipifarnib to the end of the study. In addition, patients receiving agents that are sensitive or narrow therapeutic range substrates of CYP3A4/5 are not eligible.

 Note: CYP3A4/5 inducing anti-epileptic drugs and dexamethasone for CNS tumors or metastases, on a stable dose, are allowed
- 4.2.3 Patients with known hypersensitivity to tipifarnib or any components of the tablet are not eligible.
- 4.2.4 Patients with hypersensitivity to imidazoles, such as clotrimazole, ketoconazole, miconazole and others in this drug class are not eligible.
- 4.2.5 Infection: Patients who have an uncontrolled infection are not eligible.
- 4.2.6 Patients who have received a prior solid organ transplantation are not eligible.
- 4.2.7 Patients who in the opinion of the investigator may not be able to comply with the safety monitoring requirements of the study are not eligible.

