9.1.1.1 Pharmacokinetics (PK)

Tipifarnib is rapidly absorbed after oral administration with Cmax observed within 2 to 4 hours after dosing. From population PK analyses, the absolute bioavailability of tipifarnib under fed conditions is 29.3% in cancer patients. Concomitant intake of a high fat meal increases the extent of absorption by an average of 26.8% compared with administration under fasting conditions. The PK profile of tipifarnib is consistent with a 3-compartment disposition model, with an initial fast distribution half-life (alpha) of about 36 minutes, followed by a dominant elimination half-life (beta) of about 2.4 hours, and a slower terminal half-life (gamma) of about 19 hours. Tipifarnib does not accumulate with multiple dosing. Linear PK are observed for tablets over the dose range of 100 mg through 600 mg. The steady-state volume of distribution following i.v. administration to cancer patients is 169 L. The binding of tipifarnib to plasma proteins is extensive, mostly to albumin and to a lesser extent alpha-1 acid glycoprotein and is not dependent on tipifarnib concentrations.

Tipifarnib is extensively metabolized following oral administration. Little or no tipifarnib is excreted unchanged in the urine. Less than 6% of the initial dose is recovered in feces as the parent compound. Approximately 14.4% of the administered dose is excreted in the urine as tipifarnib-glucuronide. The mean Cmax value in plasma was about 95% higher and the mean AUC12h value about 85% higher in subjects with mild hepatic impairment compared to subjects with normal liver function. These results are consistent with its extensive hepatic metabolism as the predominate route of tipifarnib elimination.

9.1.2 **Potential Drug Interactions**

Tipifarnib is a substrate for the CYP450 enzymes (mostly CYP 3A4/5) and UDP-glucuronosyltransferase (UGT). Due to the potential for drug-drug interactions, tipifarnib should not be administered with strong inhibitors or inducers of CYP3A4/5 or UGT. Additionally, CYP 2C19, 2D6, and 2E1 were observed to play a minor role in tipifarnib clearance in human liver microsomes. Population PK trials using different classes of common concomitant medications show that 1) enzyme-inducing antiepileptic drugs can significantly reduce tipifarnib plasma concentrations and 2) antifungal azoles do not alter tipifarnib clearance.

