APPENDIX II: CYP3A4 SUBSTRATES, INDUCERS, AND INHIBITORS

This is not an inclusive list. Because the lists of these agents are constantly changing, it is important to regularly consult frequently updated medical references.

CYP3A4 substrates Strong Inhibitors¹ Moderate **Strong Inducers** Moderate **Inhibitors Inducers** acalabrutinib⁵ aprepitant barbiturates bosentan atazanavir alfentanil4,5 boceprevir conivaptan carbamazepine dabrafenib amiodarone4 efavirenz clarithromycin crizotinib enzalutamide aprepitant/fosaprepitant diltiazem etravirine cobicistat fosphenytoin darunavir modafinil atorvastatin dronedarone phenobarbital axitinib delavirdine nafcillin erythromycin phenytoin bortezomib grapefruit³ fluconazole primidone rifapentin bosutinib5 grapefruit juice³ fosamprenavir rifampin budesonide5 idelalisib St. John's wort grapefruit³ buspirone⁵ grapefruit juice³ indinavir cabozantinib imatinib itraconazole calcium channel blockers ketoconazole isavuconazole lopinavir/ritonavir mifepristone cisapride citalopram/escitalopram nefazodone nilotinib cobimetinib⁵ nelfinavir verapamil conivaptan⁵ posaconazole copanlisib ritonavir crizotinib saquinavir cyclosporine⁴ telaprevir dabrafenib telithromycin dapsone voriconazole darifenacin⁵ darunavir⁵ dasatinib⁵ dexamethasone² diazepam dihydroergotamine docetaxel doxorubicin dronedarone⁵ eletriptan⁵ eplerenone⁵ ergotamine4 erlotinib estrogens

-4id-		
etoposide		
everolimus ⁵		
fentanyl ⁴		
gefitinib		
haloperidol		
ibrutinib ⁵		
idelalisib		
imatinib		
indinavir ⁵		
irinotecan		
isavuconazole ⁵		
itraconazole		
ivacaftor		
ketoconazole		
lansoprazole		
lapatinib		
losartan		
lovastatin ⁵		
lurasidone ⁵		
macrolide antibiotics		
maraviroc ⁵		
medroxyprogesterone		
methadone		
midazolam ⁵		
midostaurin ⁵		
modafinil		
nefazodone		
nilotinib		
olaparib		
ondansetron		
osimertinib		
paclitaxel		
palbociclib		
pazopanib		
quetiapine ⁵		
quinidine ⁴		
regorafenib		
romidepsin		
saquinavir ⁵		
sildenafil ⁵		
simvastatin ⁵		

sirolimus ^{4,5}		
sonidegib		
sunitinib		
tacrolimus ^{4,5}		
tamoxifen		
telaprevir		
temsirolimus		
teniposide		
tetracycline		
tipranavir ⁵		
tolvaptan ⁵		
triazolam ⁵		
trimethoprim		
vardenafil ⁵		
vemurafenib		
venetoclax ⁵		
vinca alkaloids		
zolpidem		

¹ Certain fruits, fruit juices and herbal supplements (star fruit, Seville oranges, pomegranate, gingko, goldenseal) may inhibit CYP 3A4 isozyme, however, the degree of that inhibition is unknown.

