APPENDIX III: MEDICATION DIARY FOR TIPIFARNIB

COG Patient ID:	Acc#	
Institution :		Please do not write patient names on this form.

Complete each day with the time and dose given for tipifarnib. If a dose is not due or is accidentally skipped leave that day blank. Make note of other drugs and supplements taken under the Comments section below. Take each dose with food. Tablets should be swallowed whole with a glass of water. Tablets may be chewed or crushed if necessary. If you vomit, the dose may NOT be repeated. If you miss or forget a dose, it can be taken up to 8 hours before the next dose is due. If tablet is broken and the powder of the tablets gets on skin, wash the exposed area with as much water as necessary. Inform your study doctor or nurse if that occurs. Add the dates to the calendar below and return the completed diary to your institution weekly after Cycle 1 and after each treatment cycle. Please refer to the example below. Refer to the instructions for Tipifarnib Preparation, Administration, and Safe Handling (Appendix XIII).

EXAMPLE			Number of tipifarnib tablets		Comments
	Date	Time	100 mg	300 mg	
Day 1	1/15/20	8:30 AM	2	1	He felt nauseated an hour after taking the drug but did not vomit.

Cycle #: S	tart Date: /_ End Date: /	_/_ _/_ _/_ _/_	Dose Level: 35	0 mg/m²/dose	
			# of ta	blets prescribed to take	
			100 mg	300 mg	
			AM#	AM#	1
Week 1	Date	Time	PM#	PM#	Comments (Describe any missed or extra doses,
	2000 F-2000		Number of tipifarnib tablets taken		vomiting and/or bothersome effects.)
			100 mg	300 mg	
Day 1		AM			
Day 1		PM			
Day 2		AM			
Day 2		PM			
Day 3		AM			
Duy 0		PM			
Day 4		AM			
Day :		PM			
Day 5		AM			
2, 0		PM			
Day 6	Day 6	AM			
2.1.7 0		PM			
Day 7		AM			
J -		PM			
WEEK 2	D	ates		Study drug not ed on Days 8-14	Comments (Describe any missed or extra doses, vomiting and/or bothersome effects.)

Day 8 to Day 14	7			t administered on vs 8-14	
W 12	No.	T.	Number of	tablets taken	Comments
Week 3	Date	Time	100 mg	300 mg	(Describe any missed or extra doses, vomiting and/or bothersome effects.)
Day 15		AM			
Day 13		PM			
Day 16		AM			
Day 16		PM			
Day 17		AM			
Day 17		PM			
D 10		AM			
Day 18		PM			
Day 10	D 10	AM			
Day 19		PM			
Dov. 20		AM			
Day 20		PM			
Day 21		AM			
Day 21		PM			
WEEK 4	Г	Dates		Study drug not I on Days 22-28	Comments (Describe any missed or extra doses, vomiting and/or bothersome effects.)
Day 22 to Day 28				t administered on s 22-28	

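### Section 9.1.5 tells sites that no dietary restrictions are needed, but the strong-CYP3A4-inhibitor rule read with Appendix II points to avoiding grapefruit (low severity)

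*Combined protocol and SAP*

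**What the plan says.** Section 9.1.5 (Guidelines for Administration) has tipifarnib taken by mouth twice daily with food. It then says "No dietary restrictions related to tipifarnib are required" and goes on to explain that a meal improves absorption and reduces pharmacokinetic variability. The sentence carries no exception and no pointer to the interaction sections.

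Three other places restrict strong inhibitors:

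- Section 4.2.2.5 (exclusion criteria): "Strong inducers or inhibitors of CYP3A4/5 or UGT should be avoided from 14 days prior to the 1st dose of tipifarnib", continuing to the end of the study.
- Section 7.5.1 (concomitant medications) repeats that rule.
- Section 9.1.2 (potential drug interactions): "tipifarnib should not be administered with strong inhibitors or inducers of CYP3A4/5 or UGT".

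Appendix II lists CYP3A4 substrates, inhibitors and inducers. Grapefruit and grapefruit juice each appear twice. Footnote 3 to both says that inhibition by the juice may be strong or moderate, depending on brand, concentration, dose and preparation.

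The patient diary in Appendix III says "Make note of other drugs and supplements taken under the Comments section below". It does not mention grapefruit. For preparation and handling it sends families to an Appendix XIII, which is not visible.

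**The concern.** Section 9.1.5 is where a pharmacist or nurse looks for what to tell a family about taking the tablets. Read literally, it says no food needs to be avoided. The interaction rule, applied with the protocol's own inhibitor list, gives a different answer for grapefruit. No visible passage reconciles the two, so two sites could counsel patients differently and each be able to cite the protocol.

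What is at stake is exposure. Section 9.1.2 describes tipifarnib as mainly a CYP3A4/5 substrate among the CYP enzymes, and Section 2.4.2 says the pharmacokinetics of the week-on, week-off schedule have not been studied in children. An avoidable source of variable exposure is worth closing when one clause will do it.

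**Working it through.** No figure in the plan is in question, so the check is a comparison of texts.

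**Step 1: does the avoidance rule reach beyond prescribed drugs?** The opening sentences of 4.2.2.5 and 7.5.1 concern patients receiving drugs. The avoidance sentence that follows, and the statement in 9.1.2, refer to inhibitors without that limit. Appendix II, which classifies inhibitors, includes foods. The rule can therefore be read to include a food listed as a strong inhibitor, although no visible sentence bars grapefruit by name.

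**Step 2: is grapefruit listed as a strong inhibitor?** In the text available, the columns of the Appendix II table have run together, so placement has to be inferred. The header order is substrates, strong inhibitors, moderate inhibitors, strong inducers, moderate inducers. One stretch reads "bosutinib5 grapefruit juice³ fosamprenavir rifampin budesonide5 idelalisib". Taken in header order, bosutinib is the substrate, grapefruit juice the strong inhibitor, fosamprenavir the moderate inhibitor and rifampin the strong inducer. The entries just before it fill all five columns in the same order, with grapefruit second. The next stretch contains "grapefruit³ buspirone⁵ grapefruit juice³ indinavir cabozantinib imatinib itraconazole". Its entries are slightly out of order, but alphabetical order within columns places this second pair under moderate inhibitors, between fosamprenavir and imatinib. The rebuilt rows are:

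| Substrate | Strong inhibitor | Moderate inhibitor | Strong inducer | Moderate inducer |
|---|---|---|---|---|
| bortezomib | grapefruit | fluconazole | primidone | rifapentin |
| bosutinib | grapefruit juice | fosamprenavir | rifampin | |
| budesonide | idelalisib | grapefruit | St. John's wort | |
| buspirone | indinavir | grapefruit juice | | |
| cabozantinib | itraconazole | imatinib | | |

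The count agrees: 2 foods × 2 inhibitor columns = 4 entries, and there are 4. So does footnote 3, which describes the juice as spanning the two classes. The first pair carries the point, because no visible passage restricts moderate inhibitors.

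**Step 3: set the instructions side by side.**

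| Source | Implication for grapefruit |
|---|---|
| 9.1.5 | No restriction |
| 4.2.2.5, 7.5.1 and 9.1.2, read with Appendix II | Avoid, as a listed strong inhibitor |

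The two cannot both be followed if 9.1.5 is read as worded.

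**Step 4: how large might the effect be?** The documents give no effect of grapefruit on tipifarnib exposure. The nearest evidence, in 9.1.2, is from population pharmacokinetic work: "antifungal azoles do not alter tipifarnib clearance". By the same alphabetical reading, four azoles (itraconazole, ketoconazole, posaconazole, voriconazole) stand in the strong-inhibitor column, which suggests that inhibition may matter little. However, 9.1.2 does not say which azoles were studied, and it also reports that enzyme-inducing antiepileptics can reduce tipifarnib concentrations significantly. The size therefore cannot be calculated and may be small.

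**The case against.** The best counter-argument is context. The 9.1.5 sentence stands between two statements about taking the drug with food, so it may mean only that no particular kind of meal is needed. The avoidance rule, for its part, sits under headings about medications and drug interactions, and Appendix II is a general reference list not specific to tipifarnib. On this view the conflict appears only when separate pieces are assembled. The lists of liquids for mixing crushed tablets also name orange, apple and tomato juice and never grapefruit.

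Part of this stands. The meal-content reading is plausible and keeps the severity low. It does not remove the inconsistency: the sentence is not worded that narrowly, and even at dosing it would leave grapefruit juice with the meal unrestricted. The mixing lists govern what crushed tablets go into, not what else is drunk.

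A reader might infer more than the documents support:

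- **That families are being told grapefruit is safe.** Section 9.1.5 addresses sites. The family instructions in Appendix XIII are not visible and may already warn against it. Such a warning would reduce the practical risk, though 9.1.5 would then disagree with it too.
- **That exposure would rise materially.** No figure supports this, and the azole statement points the other way.
- **That other fruits are caught as well.** Footnote 1 names star fruit, Seville oranges and pomegranate but says their degree of inhibition is unknown, so they cannot be treated as strong inhibitors.

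**Conclusion.** The inconsistency is real and of low severity. An unqualified statement to sites conflicts with a safety rule found in three other sections, once that rule is applied with the protocol's own inhibitor list. It is a matter of aligning instructions and not a design choice.

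The conclusion rests on two readings: that the avoidance rule covers inhibitors of any kind, including foods, and that the first grapefruit pair in Appendix II belongs to the strong-inhibitor column. The second is an inference on which row order, the duplicate entries and footnote 3 agree, and the typeset table can confirm it. The effect on exposure cannot be quantified from the documents and may be small. The response endpoint, sample size and analysis are untouched.

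**What to change.** Keep the 9.1.5 sentence and add a clause before its full stop: *except that grapefruit and grapefruit juice should be avoided during protocol therapy (see 7.5.1 and Appendix II)*. If Appendix XIII or other patient instructions address diet, check that they say the same.

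Limiting the clause to protocol therapy is deliberate. The strong-inhibitor window opens 14 days before the first dose, while Section 3.5 says "Protocol therapy must start no later than 7 calendar days after the date of enrollment". At least 14 − 7 = 7 days of that window therefore precede enrollment, and a food ban over the whole window would need a diet history from before the patient joined.

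The cost is one clause and a minor food restriction for patients on therapy. Endpoint, sample size, data collection and analysis do not change.

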9.1.7.1 Agent Ordering

NCI-supplied agents may be requested by eligible participating Investigators (or their authorized designee) at each participating institution. The CTEP-assigned protocol number must be used for ordering all CTEP-supplied investigational agents. The eligible participating investigators at each participating institution must be registered with CTEP, DCTD through an annual submission of FDA Form 1572 (Statement of Investigator), NCI Biosketch, Agent Shipment Form, and Financial Disclosure Form (FDF). If there are several participating investigators at one institution, CTEP-supplied investigational agents for the study should be ordered under the name of one lead participating investigator at that institution.

Note: No starter supplies will be provided. Drug orders of tipifarnib should be placed with CTEP after enrollment and treatment assignment to APEC1621M with consideration for timing of processing and shipping to

ensure receipt of drug supply prior to start of protocol therapy. If expedited shipment is required, sites should provide an express courier account through the Online Agent Order Processing (OAOP) application. Provide the patient ID number in the comment box when submitting an order request.

Submit agent requests through the PMB Online Agent Order Processing (OAOP) application. Access to OAOP requires the establishment of a CTEP Identity and Access Management (IAM) account and the maintenance of an "active" account status, "current" password, and active person registration status. For questions about drug orders, transfers, returns, or accountability call or email PMB anytime. Refer to the PMB's website for specific policies and guidelines related to agent management.

9.1.8 **Agent Accountability**

